#### **9.2.1.2 Reporting Procedures for Serious Adverse Events**

The investigator is responsible for ensuring that all serious adverse events observed by the investigator or reported by the subject that occur after signing of the informed consent through the end of study visit are recorded in the subject’s medical record and are submitted to Amgen. All serious adverse events must be submitted to Amgen within 24 hours following the investigator’s knowledge of the event via the Serious Adverse Event Report Form. Information submitted about the serious adverse event must be consistent with that recorded on the Event CRF. See [Appendix B](#) for a sample of the Serious Adverse Event Report (SAER) Form.

The investigator must assess whether the serious adverse event is possibly related to the administration of investigational product (AMG 529 or placebo). This relationship is

indicated by a “yes” or “no” response to the question: Is there a reasonable possibility that the event may have been caused by the investigational product (AMG 529 or placebo). Relatedness means that there are facts or reasons to support a relationship between investigational product and the event.

The investigator must assess whether the serious adverse event is possibly related to any study mandated activity (eg, administration of investigational product and/or study procedure, including any screening procedures). This relationship is indicated by a “yes” or “no” response to the question: Is there a reasonable possibility that the event may have been caused by a study activity (eg, administration of investigational product and/or study procedure)?

The investigator is expected to follow reported serious adverse events until stabilization or reversibility.

New information relating to a previously reported serious adverse event must be submitted to Amgen. All new information for serious adverse events must be sent to Amgen within 24 hours following knowledge of the new information. If specifically requested, the investigator may need to provide additional follow-up information, such as discharge summaries, medical records, or extracts from the medical records. Information provided about the serious adverse event must be consistent with that recorded on the Event CRF.

If a subject is permanently withdrawn from protocol-required therapies because of a serious adverse event, this information must be submitted to Amgen.

To comply with worldwide reporting regulations for serious adverse events, the treatment assignment of subjects who develop serious, unexpected, and related adverse events may be unblinded by Amgen before submission to regulatory authorities.

Amgen will report serious adverse events and/or suspected unexpected serious adverse reactions as required to regulatory authorities, investigators/institutions, and IRBs/IECs in compliance with all reporting requirements according to local regulations and good clinical practice.

The investigator is to notify the appropriate IRB/IEC of serious adverse events occurring at the site and other adverse event reports received from Amgen, in accordance with local regulatory requirements and procedures.

### **9.2.1.3 Reporting Serious Adverse Events After the Protocol-required Reporting Period**

There is no requirement to monitor study subjects for serious adverse events following the protocol-required reporting period or after the end of study. However, these serious adverse events can be reported to Amgen. In some countries (eg, European Union [EU] member states), investigators are required to report serious adverse events that they become aware of after end of study. If serious adverse events are reported, the investigator is to report them to Amgen within 24 hours following the investigator's knowledge of the event.

Serious adverse events reported outside of the protocol-required reporting period will be captured within the safety database as clinical trial cases for the purposes of expedited reporting.

See [Appendix B](#) for a sample of the Serious Adverse Event Report (SAER) Form.

## **9.3 Pregnancy and Lactation Reporting**

If a female subject becomes pregnant, or a male subject fathers a child, while the subject is taking protocol-required therapies, AMG 529 or placebo, report the pregnancy to Amgen Global Patient Safety as specified below.

In addition to reporting any pregnancies occurring during the study, investigators should report pregnancies that occur through 90 days after the last dose of AMG 529.

The pregnancy should be reported to Amgen Global Patient Safety within 24 hours of the investigator's knowledge of the pregnancy. Report a pregnancy on the Pregnancy Notification Worksheet ([Appendix C](#)). Amgen Global Patient Safety will follow-up with the investigator regarding additional information that may be requested.

If a female subject becomes pregnant during the study, the investigator should attempt to obtain information regarding the birth outcome and health of the infant.

If the outcome of the pregnancy meets a criterion for immediate classification as a Serious Adverse Event (eg, female subject experiences a spontaneous abortion, stillbirth, or neonatal death or there is a fetal or neonatal congenital anomaly) the investigator will report the event as a Serious Adverse Event.

If a female subject breastfeeds while taking protocol-required therapies report the lactation case to Amgen as specified below.

In addition to reporting a lactation case during the study, investigators should report lactation cases that occur through 90 days after the last dose of protocol-required therapies.

Any lactation case should be reported to Amgen Global Patient Safety within 24 hours of the Investigator's knowledge of event. Report a lactation case on the Lactation Notification Worksheet ([Appendix D](#)). Amgen Global Patient Safety will follow-up with the investigator regarding additional information that may be requested.

If a male subject's female partner becomes pregnant, the investigator should discuss obtaining information regarding the birth outcome and health of the infant from the pregnant partner.

## **10. STATISTICAL CONSIDERATIONS**

### **10.1 Study Endpoints, Analysis Sets, and Covariates**

#### **10.1.1 Study Endpoints**

##### **10.1.1.1 Primary Endpoints**

- Subject incidence of treatment-emergent adverse events
- Safety laboratory analytes, vital signs, and ECGs

##### **10.1.1.2 Secondary Endpoints**

- AMG 529 PK parameters including, but not limited to, maximum observed concentration ( $C_{max}$ ), the time of maximum observed concentration ( $t_{max}$ ), and area under the concentration-time curve (AUC)
- Pharmacodynamic parameters:
  - ALP levels
  - Lipid levels (ie, total cholesterol, LDL-C, HDL-C, and triglycerides)

##### **10.1.1.3 Exploratory Endpoints**

- Measurements of potential biomarkers
- Measurements of alkaline phosphatase isoenzymes
- Measurements of ApoA1 and ApoB
- Subject incidence of anti-AMG 529 antibodies, if measured
- AMG 529 exposure (eg, dose,  $C_{max}$ , and/or AUC) and ALP change from baseline

#### **10.1.2 Analysis Sets**

For all analyses, subjects will be analyzed according to the dose and treatment they received, not the dose and treatment to which they were randomized.

#### **10.1.2.1 Safety Analysis Set**

The safety set will consist of all study subjects who receive at least one dose of AMG 529 or placebo.

#### **10.1.2.2 Pharmacokinetic Analysis Set**

The PK analysis set will consist of all subjects for whom at least one PK parameter or endpoint can be reliably estimated.

#### **10.1.2.3 Pharmacodynamics Analysis Set**

The PD analysis set will contain all study subjects who receive at least one dose of AMG 529 or placebo and for whom at least 1 PD parameter has a baseline and at least 1 post baseline measurement available.

#### **10.1.3 Covariates and Subgroups**

Baseline values may be used as a covariate in analyses. For any variable, unless otherwise defined, baseline is defined as the last assessment taken prior to the first administration of AMG 529 or placebo.

No subgroup analyses are planned. Within each cohort, subjects will be randomized so that 6 subjects receive AMG 529 and 2 subjects receive placebo in each cohort. Data from placebo-treated healthy subjects will be pooled across the cohorts for analysis.

#### **10.2 Sample Size Considerations**

The sample size is based on practical considerations. Approximately 48 healthy subjects will enroll to participate in cohorts 1 through 6 of this study. With 6 subjects receiving AMG 529 in a cohort there is a 74% chance of detecting an adverse event with a true incidence of 20%. With 36 subjects receiving AMG 529 there is an 84% chance of detecting an adverse event with a true incidence of 5%.

#### **10.3 Access to Individual Subject Treatment Assignments by Amgen or Designees**

Blinded individuals will not have access to unblinded information until the study is formally unblinded. Amgen staff and their designees involved in the study will not be blinded, but will only be given treatment assignments when there is a need to use the information for analysis, discussion and internal decision making. The Amgen Medical Monitor will be unblinded to treatment assignment throughout the duration of the study. Access to treatment assignments and other restricted data are described in Amgen standard documents. Unblinded individuals are to ensure unblinding and potentially

unblinding information should not be distributed to the investigators or subjects prior to the study being formally unblinded.

#### **10.4 Planned Analyses**

##### **10.4.1 Dose Level Review Meeting (DLRM)**

The DLRM members are responsible for dose level decisions. The key objectives of the DLRM are to review data, monitor safety, and make dose change decisions. The DLRM members will consist of the principal investigator or designee, the unblinded Amgen Medical Monitor, Amgen Global Safety Officer or designee, Amgen Clinical Research Study Manager or designee, and a Biostatistics representative or designee. Additional members may be added as needed (eg, PK scientist). Except for the unblinded Amgen Medical Monitor who will review data in an unblinded manner, DLRMs will be conducted in a blinded manner.

##### **10.4.2 Primary Analysis**

The primary analysis will occur after the database lock following last subject last visit.

##### **10.4.3 Final Analysis**

The primary analysis will be the final analysis.

#### **10.5 Planned Methods of Analysis**

##### **10.5.1 General Considerations**

Descriptive statistics will be provided for selected demographics, safety, PK, and PD data. Data for subjects receiving placebo will be combined across all cohorts, except for adverse events where the combined SC cohorts will be summarized separately from the IV cohort. Descriptive statistics on continuous measurements will include means, medians, standard deviations, and ranges, while categorical data will be summarized using frequency counts and percentages. Data will be summarized by treatment group and at each time point when samples are collected.

The number and percent of subjects reporting any treatment-emergent adverse events will be tabulated by system organ class and preferred term and will be further classified by relationship to treatment.

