## **Investigational Product**

### **Amgen Investigational Product Dosage and Administration:**

A total of 48 subjects will be randomized to receive 1 of 6 doses of AMG 529 or equivalent volume of placebo. Subjects will receive AMG 529 in fixed doses of 21, 70, 210, 420, or 700 mg SC, or 70 mg IV.

The planned dose escalation schedule may be modified based on treatment-emergent data (safety and/or PK). Dose adjustments (if any) will be made on a treatment cohort and not on an individual basis, and will be agreed upon by Amgen in coordination with the principal investigator.

**Control Group:** The control group will be those subjects who will be administered placebo. Within each cohort, 2 subjects will receive an equivalent volume of placebo.

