### 2.3 Risk Assessment

To date, AMG 529 has not been administered to human subjects; therefore, no clinical data are available. This is the first single dose study proposed in human subjects with AMG 529. The assessment of potential side effects of AMG 529 is based on the pre-clinical studies conducted to date ([Section 2.2.3](#)) and the literature.

In addition to the cardioprotective phenotype, the *ASGR1* del12 variant was associated with elevated levels of ALP (50.1% change; 95% CI, 42.9 to 57.2;  $p=3.6 \times 10^{-63}$ ) and vitamin B12 (16.6% change; 95% CI, 11.5 to 21.5;  $p=3.1 \times 10^{-12}$ ), proposed to result from reduced clearance by ASGPR ([Nioi et al, 2016](#)). Increased GGT (10.3% change; 95% CI 1.7 to 19.2;  $p=0.015$ ) and decreased albumin (-0.72 g/L; 95% CI -1.37 to 0.06;  $p=0.033$ ) were also observed, but did not reach genome-wide significance ( $p=5 \times 10^{-8}$ ). There was no association between the del12 variant and ALT (5.8% change; 95% CI -0.4 to 12.2;  $p=0.065$ ), AST (4.1% change; 95% CI -2.9 to 11.4;  $p=0.095$ ), or bilirubin (3.7% change; 95% CI -2.6 to 10.4;  $p=0.25$ ), suggesting that the increase in ALP was not likely due to underlying liver disease.

Increases in ALP and potentially GGT are expected with AMG 529 administration due to reduced clearance of these desialylated molecules from the circulation and are not indicative of hepatotoxicity. Alkaline phosphatase and GGT, along with other assessments of liver function (AST, ALT, bilirubin and albumin), will be monitored in this FIH study. The expectation is that only increases in ALP and potentially GGT will occur without clinically relevant increases in the other liver function tests.

Minimal reductions in PT were noted in the 14-day toxicology study in cynomolgus monkeys. While the clinical relevance of this finding is unclear, PT, international normalized ratio (INR), and aPTT will be evaluated in all subjects.

As with any therapeutic antibody, administration of AMG 529 may result in systemic (eg, hypersensitivity) and local (eg, injection site) reactions, and immunogenicity (ie, the development of anti-AMG 529 antibodies). A sentinel dosing strategy will thus be used

for all cohorts of this study to mitigate the chances of subjects experiencing unexpected adverse events resulting from a single dose of AMG 529.

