## 3. EXPERIMENTAL PLAN

### 3.1 Study Design

This is a phase 1, randomized, double-blind, placebo-controlled, ascending single-dose study in healthy subjects.

Approximately 48 subjects will enroll in 1 of 6 dose cohorts (8 per cohort). For cohorts 1, 2, 3, 4, and 5, eight (8) subjects will be randomized to receive AMG 529 or placebo SC in a 3:1 ratio at dose levels of 21, 70, 210, 420, and 700 mg, respectively.

In cohort 6, eight (8) subjects will receive AMG 529 or placebo IV in a 3:1 ratio at a dose level of 70 mg.

For all cohorts, the first 2 subjects (sentinel pair) will be randomized such that 1 subject will receive AMG 529 and 1 subject will receive placebo, and observed for at least 24 hours before the remaining subjects in the cohort are dosed, provided there are no safety or tolerability concerns as assessed by the principal investigator.

Escalation to a higher dose cohort will only proceed when the previous dose regimen has been found to be safe and reasonably tolerated based on available safety and laboratory data through study day 15 for all subjects and upon unanimous decision at the Dose Level Review Meeting (DLRM). Enrollment can be initiated in cohort 5 and cohort 6 after the dose regimen in cohort 4 has been found to be safe and well tolerated. Cohort 6 will start enrollment after the completion of cohort 5 enrollment.

The overall study design is described by a [study schema](#) at the end of the protocol synopsis section.

The study endpoints are defined in [Section 10.1.1](#).

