#### **6.2.1 Amgen Investigational Product AMG 529 and Placebo**

AMG 529 for SC and IV administration will be manufactured and packaged by Amgen Inc. and distributed using Amgen clinical study drug distribution procedures.

AMG 529 is provided in 5 mL sterile vials filled with a 1 mL deliverable volume of 70 mg/mL AMG 529. Placebo will be presented in identical containers and stored/packaged the same as AMG 529.

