9.1 General Considerations

Descriptive statistics will be provided for selected demographics, safety, PK, and PD data. Data for subjects receiving placebo will be combined across all cohorts, except for adverse events where the combined SC cohorts will be summarized separately from the IV cohort. Descriptive statistics on continuous measurements will include means, medians, standard deviations, and ranges, while categorical data will be summarized using frequency counts and percentages. Data will be summarized by treatment group and at each time point when samples are collected. The number and percent of subjects reporting any treatment-emergent adverse events will be tabulated by system organ class and preferred term and will be further classified by relationship to treatment.

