9.6 Safety Analyses

9.6.1 Analyses of Primary Safety Endpoint(s)

9.6.2 Adverse Events and Disease-related Events

All subjects who receive a dose of AMG 529 or placebo will be included in the safety analyses. Subject incidence of all treatment-emergent adverse events will be tabulated by system organ class and preferred term according to the medical dictionary for regulatory activities terminology. Tables of adverse events, fatal adverse events, and serious adverse events will also be provided if observed.

The Medical Dictionary for Regulatory Activities (MedDRA) version 19.0 or later will be used to code all adverse events to a system organ class and a preferred term. The subject incidence of adverse events by treatment group will be summarized for all treatment emergent, serious treatment emergent, treatment related, serious treatment related, those leading to withdrawal of investigational product, severe, life threatening and fatal adverse events.

The severity of each adverse event will be graded using protocol defined criteria. Subject incidence of treatment emergent events and treatment related treatment emergent events will further be summarized by worst severity grade. Subject incidence of all treatment emergent, serious treatment emergent, treatment emergent events leading to withdrawal of investigational product, and treatment emergent fatal adverse events will further be tabulated by system organ class and preferred term in descending order of frequency.

The above adverse event tables will not be created if two or fewer subjects in the study experience the adverse event. Narratives of any on-study deaths, serious treatment-emergent adverse events, including early withdrawals due to adverse events, also will be provided should they occur.

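### Pooling all SC placebo for adverse events sets aside the volume match within cohorts; if injection-site reactions depend on volume, the tables could show a volume effect as a dose trend

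*Protocol*

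**What the plan says.** Five SC cohorts are dosed "at dose levels of 21, 70, 210, 420, and 700 mg, respectively" (Protocol 3.1). In every cohort "subjects will be randomized so that 6 subjects receive AMG 529 and 2 subjects receive placebo in each cohort" (Protocol 10.1.3), which gives 10 SC and 2 IV placebo subjects in all.

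On the product, Protocol 6.2.1 states: "AMG 529 is provided in 5 mL sterile vials filled with a 1 mL deliverable volume of 70 mg/mL AMG 529". On the control, the synopsis states: "Within each cohort, 2 subjects will receive an equivalent volume of placebo".

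For adverse events, placebo is pooled over the SC cohorts and only the IV placebo is kept apart: "except for adverse events where the combined SC cohorts will be summarized separately from the IV cohort" (Protocol 10.5.1). SAP 9.1 repeats the rule in the same terms. The display is by treatment group: "The subject incidence of adverse events by treatment group will be summarized for all treatment emergent" (SAP 9.6.2).

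Protocol 2.3 names "local (eg, injection site) reactions" among the risks of giving a therapeutic antibody. Neither document plans an adverse-event display of placebo by cohort or volume, or a separate summary of injection-site reactions.

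**The concern.** Randomisation within a cohort balances injected volume between AMG 529 and placebo, because both arms of that cohort receive the same volume. Pooling placebo over cohorts 1 to 5 removes that balance from the display. Volume rises with dose across the AMG 529 columns, while the single placebo column stands for a fixed mixture of volumes. Any dependence of local reactions on volume would then appear in the contrast with placebo as a trend with dose.

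Safety and tolerability over ascending doses is the primary objective, and incidence of treatment-emergent adverse events is a primary endpoint. A misread local-tolerability trend would therefore sit in the main results of the study report. The subjects who could help separate drug from volume are already enrolled and observed, but their cohort is not visible in the planned tables.

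**Working it through.** **The plan's own figures.** The documents give no figure for this point. Their only related arithmetic is the chance of seeing at least one event, 1-(1-p)^n. For n=6 and p=0.20 this is 1-0.8^6 = 73.8% (74% stated). For n=36 and p=0.05 it is 1-0.95^36 = 84.2% (84% stated). Both reproduce.

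**Volumes.** Inputs are the SC doses (Protocol 3.1) and the 70 mg/mL concentration (Protocol 6.2.1), assuming undiluted dosing. Volume = dose/70:

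- 21 mg: 0.3 mL
- 70 mg: 1 mL
- 210 mg: 3 mL
- 420 mg: 6 mL
- 700 mg: 10 mL

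The range is 10/0.3 = 33-fold. With 2 placebo subjects per cohort, the mean volume in the pool is (0.3+1+3+6+10)/5 = 4.06 mL.

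**Effect of pooling, as an illustration.** Assume the drug is inert, so the true reaction rate depends only on volume v and is equal in both arms of a cohort. The pooled placebo rate is the plain mean of the five cohort rates, and the apparent effect is the cohort rate minus the pooled rate. All reaction rates below are assumptions, because the documents give none. Three shapes were tried:

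- linear: lo + (hi-lo)(v-0.3)/9.7
- logarithmic: lo + (hi-lo) ln(v/0.3)/ln(10/0.3)
- constant risk p per mL: 1-(1-p)^v

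| Assumed rates | Cohorts 1 to 5, % | Pooled placebo, % | Shift at 21 mg, points | Shift at 700 mg, points |
|---|---|---|---|---|
| Linear, 5 to 20% | 5.0, 6.1, 9.2, 13.8, 20.0 | 10.8 | -5.8 | +9.2 |
| Linear, 5 to 40% | 5.0, 7.5, 14.7, 25.6, 40.0 | 18.6 | -13.6 | +21.4 |
| Linear, 10 to 50% | 10.0, 12.9, 21.1, 33.5, 50.0 | 25.5 | -15.5 | +24.5 |
| Log, 5 to 20% | 5.0, 10.2, 14.8, 17.8, 20.0 | 13.6 | -8.6 | +6.4 |
| Log, 5 to 40% | 5.0, 17.0, 28.0, 34.9, 40.0 | 25.0 | -20.0 | +15.0 |
| Log, 10 to 50% | 10.0, 23.7, 36.3, 44.2, 50.0 | 32.8 | -22.8 | +17.2 |
| 2% per mL | 0.6, 2.0, 5.9, 11.4, 18.3 | 7.6 | -7.0 | +10.7 |
| 5% per mL | 1.5, 5.0, 14.3, 26.5, 40.1 | 17.5 | -16.0 | +22.6 |
| Flat, 20% | 20 throughout | 20 | 0 | 0 |

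Wherever the rate rises with volume, the direction is the same. The size depends entirely on the assumed rates.

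**What matched placebo can show.** At a 20% reaction rate, the chance of seeing at least one placebo event is 1-0.8^2 = 36% with 2 subjects and 1-0.8^10 = 89% with 10. At a 40% rate, two matched placebo subjects would both be free of reactions with probability 0.6^2 = 36%.

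**The case against.** The strongest case against is that this is a presentation matter with an unproven mechanism. Most of that stands, and it rules out several stronger readings.

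- A reader might infer that local tolerability is confounded with volume. The documents report no relation between volume and reactions. The volumes themselves are derived: Protocol 6.1 leaves preparation and administration to an external manual, and the number of injections per dose is not stated. The claim has to stay conditional.
- A reader might infer that reactions at 21 and 70 mg would be understated. Each AMG 529 column still shows its own incidence. Only the informal contrast with placebo can shift, and no test, margin or decision rule is attached to it.
- A reader might infer that escalation or stopping is at risk. The dose-level review proceeds cohort by cohort, the Grade 2 stopping rule counts reactions within a cohort, and the Medical Monitor is unblinded throughout (Protocol 6.2.1.2 and Table 3). None of these uses the pooled column.
- A reader might infer that the sponsor separates IV from SC placebo because the procedure affects adverse events, and should do the same for volume. Neither document gives a reason for that split.
- A reader might want local tolerability judged against matched placebo alone. Two subjects cannot carry that. Under the 40% scenario they show no reaction 36% of the time, which would make an inert 700 mg dose look worse than it does against the pool.

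The volume argument also does not reach systemic events, for which pooling is reasonable. One gap survives these objections: no planned adverse-event output lets a reader see local reactions against placebo of the same volume.

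**Conclusion.** The point holds in conditional form. The pooling rule, the volume match within cohorts and the absence of any adverse-event display by cohort for placebo are all in the documents. The 0.3 to 10 mL range follows from them if SC dosing is undiluted. If injection-site reactions rise with volume, the side-by-side tables could make a volume effect look like a drug dose trend. In the scenarios tried, the shift is +6.4 to +24.5 points at 700 mg and -5.8 to -22.8 points at 21 mg. If they do not depend on volume, it is zero. The true size cannot be known from the documents. The consequence is confined to how the end-of-study descriptive tables are read, so this is an inexpensive improvement and not a flaw in the design or in the safety oversight.

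**What to change.** Keep the pooled SC placebo column for all adverse events. Add to SAP 9.6.2 one descriptive table of injection-site reactions by SC cohort, with AMG 529 (n=6) beside that cohort's volume-matched placebo (n=2), and say that it is to be read alongside the pooled column. SAP 9.6.2 omits adverse-event tables when two or fewer subjects have the event, so provide a listing by cohort if events are that few. Specify this before unblinding, so that the comparator is not chosen after the data are seen.

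The addition should stop there. It needs no grouping of placebo by volume: a group of 3 mL or more would still mix 3, 6 and 10 mL. It needs no extension to overall adverse events on volume grounds, and no rule making the matched placebo the sole basis for interpretation.

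The cost is one extra output from data already collected, with no change to dosing, sample size or conduct. The downside is very small placebo cells: with 2 subjects and a 20% rate there is only a 36% chance of seeing any event, so the table is descriptive only.
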